To date, no comparison of cardiac rehabilitation efficacy and acute exercise responses has been made between patients with PAD and patients with CAD. Considering some of the parallels between the two conditions, as they are both atherosclerotic conditions, and the strong recommendations for exercise in both populations, it is worthwhile to compare the efficacy of cardiac rehabilitation responses. It is also unclear if the magnitude of response for PAD patients is dependent on biological sex and clinical presentation as this may influence the development of exercise prescriptions. This proposed study, which is in the process of being registered with clinicaltrials.gov, hopes to address these gaps in the literature.

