#### 3.1.2 Secondary objectives

The second objective of this proposed study is to determine if the magnitude of responses to cardiac rehabilitation for patients with PAD are dependent on biological sex or type of PAD (asymptomatic, post-surgical intervention, or intermittent claudication).

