#### 3.2 Study hypothesis

The primary hypothesis is that patients with CAD will have greater improvements in  $VO_2\text{peak}$  and 6-minute walk test compared to patients with PAD (Lucini et al., 2002; Parmenter, et al., 2015). However, considering the walking limitations patients with PAD often have and the improvements observed with exercise training (Milani & Lavie, 2007; Novakovic et al., 2016), it is hypothesized that patients with PAD will have greater improvements in the WIQ and QOL compared with patients with CAD. Furthermore, a secondary hypothesis that the magnitude of response for patients with PAD will be dependent on biological sex and type of PAD. Lastly, it is hypothesized that patients with PAD on average will have a greater exercising heart rate, rating of perceived exertion and rating of pain severity compare to patients with CAD.

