## **5.0 Selection of Subjects**

### 5.1 Subject inclusion criteria.

Inclusion criteria will include patients over the age of 18 that have been diagnosed with lower extremity PAD or CAD. Patients with concomitant CAD and PAD will also be included in the study. Group allocation will be based on referring diagnosis. In addition, patients must be able to access and participate in the cardiac rehabilitation program at the TRI.

In order to compare patients with PAD to patients with CAD and to control for confounding variables, matching will be based on biological sex, age ( $\pm 5$  years), presence of diabetes (yes or no), smoking status (current, previous, never), and cardiac rehabilitation supervisor.

Patients diagnosed with PAD from the University Health Network and Sunnybrook Hospital will be referred by vascular surgeons to the TRI Rumsey Centre for cardiac rehabilitation. Patients with CAD referred to cardiac rehabilitation will be identified through consented chart review and invited to participate in the study.

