## **8.0 Statistics**

### **8.1 A description of the statistical methods to be employed**

Primary analysis to determine if patients with CAD or patients with PAD have greater improvements in  $VO_2$ peak, 6MWT, WIQ, and QOL will be tested with a series of two factor 2 (time: Baseline, End) by 2 (group: PAD, CAD) analyses of variances with Tukey's Honest Significant Difference (HSD) test for post-hoc corrections. This analysis will include patients who attended  $>70\%$  of on-site cardiac rehabilitation sessions. An intention-to-treat analysis will be conducted to include patients who attended less than 70% of the cardiac rehabilitation program sessions.

The secondary hypothesis that the magnitude of responses for patients with PAD will be dependent on biological sex will be tested through conducting a 3 factor 2 (time: Baseline, End) by 2 (group: PAD, CAD) by 2 (sex: men, women) analysis of variance. In addition to determine if the magnitude of responses are dependent on clinical presentation of PAD, a 2 factor 2 (time: Baseline, End) by 2 (type: asymptomatic, post-surgical intervention, IC) analysis of variance will be conducted.

To determine if PAD patients have greater exercising heart rate, rating of perceived exertion (Borg scale), rating of pain severity (, and training volumes than CAD patients, tertiary analysis will involve independent t-tests for these variables.

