### **8.2 The number of subjects planned to be enrolled**

Sample size calculations were conducted using an alpha of 5% and a power of 0.8. Calculations were based on the primary and secondary variables of interest ( $VO_2$ peak

Comparing the efficacy of cardiac rehabilitation for patients with peripheral artery disease to patients with coronary artery disease/Protocol #03

and 6MWT distance) for PAD and CAD patients. To be conservative, the largest sample size (6MWT) was selected.

Previous literature has found that patients with PAD undergoing exercise training compared to PAD patients who did not undergo exercise training had improvements in the 6MWT of 34.9m (95 % CI 25.6–44.1 m,  $P<0.00001$ ) (Parmenter et al., 2015). In contrast, patients with CAD had improvements of  $29.6\pm12$ m following exercise training (Jaureguizar et al., 2016). Clinically significant changes have been defined as 20m for the 6MWT (Perera et al., 2006). A difference of 10 meters between groups is a conservative average between what is observed in the literature and the defined clinically significant change. The sample size calculation for a power of 0.8 would be 23 participants per group. Accounting for a 20% drop out, 28 patients with CAD and 28 patients with PAD will be recruited. Statistical significance will be set at a  $P$  value of 0.05.

A sample size of 28 participants per group is powered to detect a difference of 1.6 ml/kg/min between groups for VO2peak.

8.3 Procedure for accounting for missing, unused, and spurious data.

If data variables are missing, the whole participant data set will be excluded from the main statistical analysis. If some data is available, the participant's data will be included in the intention to treat analysis.

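### The sex hypothesis is about PAD patients only, but Section 8.1 tests it with a PAD-plus-CAD three-factor ANOVA and names no deciding term; a lesser point is that the matching is not carried into the analysis

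*Combined protocol and SAP*

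**What the plan says.** The sex question is put in terms of PAD patients wherever it appears:

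- Section 2.1: "It is also unclear if the magnitude of response for PAD patients is dependent on biological sex and clinical presentation".
- Section 3.1.2: the aim is to "determine if the magnitude of responses to cardiac rehabilitation for patients with PAD are dependent on biological sex or type of PAD".
- Section 3.2: "a secondary hypothesis that the magnitude of response for patients with PAD will be dependent on biological sex and type of PAD".
- Section 8.1: "The secondary hypothesis that the magnitude of responses for patients with PAD will be dependent on biological sex will be tested through conducting" a three-factor model, time "by 2 (group: PAD, CAD) by 2 (sex: men, women) analysis of variance".

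Section 8.1 names no term or contrast of that model as the test. Tukey's HSD is mentioned only for the primary two-factor ANOVAs. The companion question on PAD type has no group factor, so it is in effect PAD-only. It is written as time "by 2 (type: asymptomatic, post-surgical intervention, IC) analysis of variance will be conducted", which declares two levels and lists three.

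On matching, Section 5.1 says: "In order to compare patients with PAD to patients with CAD and to control for confounding variables, matching will be based on biological sex", followed by age, diabetes, smoking status and supervisor. Section 11.1.1 describes finding a CAD match for a PAD participant. Sections 2.4 and 11.1 give the matching factors without smoking. The group comparisons in Section 8.1 are time by group ANOVAs and independent t-tests, with no pair term and no matching factor.

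**The concern.** Each candidate term of the three-factor model answers a different question:

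- **Time by group by sex:** does the sex effect on response differ between PAD and CAD?
- **Time by sex:** is there a sex effect on response, averaged over the two diseases?
- **Time by sex within PAD:** does response in PAD depend on sex? This is the stated hypothesis.

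If the three-way term decides, a sex effect of the same size in both diseases is missed although the PAD hypothesis is true. If either omnibus term decides, an effect present only in CAD can produce significance although the PAD hypothesis is false. That is not a type I error of the term itself; it is a correct rejection of a different null hypothesis, read as an answer to this one. With the deciding term left open, the choice can also be made after the results are seen.

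The matching is a smaller matter. It is the plan's stated control for confounding in a non-randomised comparison. The attendance rule (Section 5.2), the discarding of withdrawn patients' data (Section 5.3) and the whole-participant exclusion for missing data (Section 8.3) can each remove one member of a pair. Nothing says what then happens to the other.

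**Working it through.** **The plan's own figure.** Section 8.2 uses a 10 m difference in 6MWT change, alpha 5% and power 0.8. The only spread given is the ±12 m for CAD, read here as an SD. Two-sided, by the normal approximation:

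n = 2 × (1.960 + 0.842)² × 12² / 10² = 22.6, so 23 per group.

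This matches "The sample size calculation for a power of 0.8 would be 23 participants per group", and 23 × 1.2 = 27.6 gives the 28 recruited. The calculation is for the group comparison; the section gives none for the sex question.

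**Inputs for the sex test.** 23 evaluable patients per group (Section 8.2). The sex split is not given, so 12/11, 15/8 and 18/5 are shown, the same in both groups because sex is matched. Effects are in SD of change, with equal SDs, independent patients and two-sided 5% tests.

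**Standard errors on change scores.** With v = 1/n_men + 1/n_women in each group:

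- within PAD: √v
- three-way: √(2v)
- time by sex, averaged over groups: √(2v)/2

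At 12/11, v = 1/12 + 1/11 = 0.174, giving 0.417, 0.590 and 0.295. At 18/5, v = 0.256, giving 0.506, 0.715 and 0.357. Rejection probabilities come from the non-central t with 42 df (46 − 4). For the within-PAD contrast the range covers 21 df (PAD-only error) to 42 df (pooled error).

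**Probability of a significant result, 1 SD sex effect**

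| Truth | Term | 12/11 | 15/8 | 18/5 |
|---|---|---|---|---|
| Same in PAD and CAD | Three-way | 5% | 5% | 5% |
| | Within PAD | 63–65% | 59–61% | 47–49% |
| | Pooled time by sex | 91% | 88% | 78% |
| CAD only | Three-way | 38% | 35% | 28% |
| | Within PAD | 5% | 5% | 5% |
| | Pooled time by sex | 38% | 35% | 28% |

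The three-way and pooled terms agree in the CAD-only case because the pooled estimate is halved and so is its standard error. At 12/11 that 38% becomes 13% for a 0.5 SD effect and 51% for 1.2 SD. A shared 0.5 SD effect gives the within-PAD contrast 21–22% power at 12/11. Simulation (100,000 runs) agrees: CAD-only three-way 0.379 and 0.279, shared within-PAD 0.648 and 0.490, at 12/11 and 18/5.

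**Detectable effects at 80% power.** Within PAD: 1.20–1.23 SD at 12/11 and 1.45–1.49 SD at 18/5. Multiplied by 12 m, if that SD also holds in PAD, these are about 14–15 m and 17–18 m. The three-way term needs a PAD–CAD difference in sex effects of 1.69 SD (12/11) or 2.05 SD (18/5).

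**Matching.** With the plan's 20% loss, independent in each arm, 0.8² × 28 = 17.9 pairs stay intact on average. If exactly 22 remain per arm, the hypergeometric distribution gives 16, 17 or 18 intact pairs with probability 20%, 42% and 29%. Simulating the unpaired test on 18 pairs plus 4 unpaired patients per arm gives a true size of 5.0%, 4.2%, 3.4% and 2.5% for assumed within-pair correlations of 0, 0.1, 0.2 and 0.3. The planned test is therefore valid, or conservative if pairs correlate positively.

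**The case against.** The strongest reply is that nothing is wrong with the model: the within-PAD contrast can be estimated from it, and following an interaction with simple effects is ordinary practice. That is right about the model. But Section 8.1 promises no such step, and its post-hoc procedure is attached to other analyses. The defect is the unnamed contrast.

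A second reply is that comparing PAD with CAD is the study's purpose, so asking whether sex-dependence differs between them is coherent. It is a reasonable exploratory question, but not the one stated in Sections 2.1, 3.1.2, 3.2 and 8.1.

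Third, the 38% depends on a large effect in CAD and none in PAD, and the documents give neither a sex effect nor a sex split. This stands: at 12/11 the figure falls to 13% at 0.5 SD and about 7% at 0.25 SD. The numbers show how far the terms can disagree; they do not forecast this trial.

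Fourth, the recommended contrast is itself weakly powered, and the hypothesis is secondary. Both are true and limit the weight of the point. They do not justify testing a different hypothesis.

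On matching, the objection largely succeeds. The unpaired test does not inflate error, the bias from broken pairs cannot be computed from the documents, and a sensitivity analysis is enough. The two-level label and the smoking discrepancy are accurate but minor.

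**Conclusion.** The concern holds, and the plan should be changed. As written, the sex hypothesis has no defined test, and neither omnibus term of the planned model answers it. For the same shared 1 SD effect at a 12/11 split, the chance of a significant result is 5%, 63–65% or 91% depending on the term chosen. For an effect confined to CAD, two of the three candidates reject 38% of the time at that split (28% at 18/5) when the PAD hypothesis is false. These figures rest on 23 evaluable patients per group, equal sex splits, equal SDs and assumed effect sizes. The mismatch between hypothesis and test rests on the text alone.

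The primary comparison and the sample size are not affected by the sex point. The matching point is secondary: it concerns control of confounding, not error rate or power.

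**What to change.** - **Sex hypothesis.** Prespecify the time by sex contrast within PAD as the deciding test, from a PAD-only two-by-two ANOVA or as a contrast from the three-factor model, and state which error term is used. Report it with a 95% CI. Keep the three-way term as exploratory.
- **PAD type.** Correct the factor to three levels: a 2 × 3 model with a 2-df interaction.
- **Matching.** Add a sensitivity analysis of the group comparisons that keeps all participants and adjusts for the matching factors, for example a linear model of change with residual-df t tests. If a matched-set effect is added, name a small-sample df method such as Satterthwaite or Kenward-Roger. Keep a pair identifier and the supervisor in the dataset.
- **Consistency.** Reconcile smoking as a matching factor between Section 5.1 and Sections 2.4 and 11.1.

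The first two changes cost one sentence and one label. The price of the right contrast is power: when the effect is shared, 63–65% against 91% for the pooled term at 12/11, and 47–49% against 78% at 18/5. A null result in PAD will be inconclusive for moderate effects, and the CI should be read that way. The adjusted analysis is a little more work. If the matching factors do not predict change, its power for 10 m with SD 12 m and 22 per arm is 74–75% against 77% unadjusted, assuming 2 to 5 supervisors.

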## Comparing the efficacy of cardiac rehabilitation for patients with peripheral artery disease to patients with coronary artery disease/Protocol #03

patient populations. As well, differences in responses to cardiac rehabilitation based on biological sex and clinical presentation of PAD are not well established. With the newly implemented cardiac rehabilitation program specifically for patients with PAD at TRI, this proposed study is aligned well to address these gaps in the literature. This trial will be conducted in compliance with the protocol described below as well as ICH and GCP standards.

This research is important as the findings from this study may provide further support for the implementation of PAD-specific exercise rehabilitation programs. Determining the efficacy of cardiac rehabilitation for patients with PAD can also help contribute to the understanding of PAD in relation to exercise. Lastly, determining if the magnitude of response is dependent on biological sex and presentation of PAD can help guide future research in determining optimal exercise prescriptions

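### The secondary hypothesis on sex and PAD type has no deciding outcome, no multiplicity rule and a conflicting and/or wording: about 30% false-positive chance if any of eight tests counts, about 10% or 1–3% under narrower readings

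*Combined protocol and SAP*

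**What the plan says.** All references are to the combined protocol and SAP.

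- Section 3.1.2 (secondary objectives) sets out to "determine if the magnitude of responses to cardiac rehabilitation for patients with PAD are dependent on biological sex or type of PAD".
- Section 3.2 (hypothesis) states "a secondary hypothesis that the magnitude of response for patients with PAD will be dependent on biological sex and type of PAD". The conjunction has changed from *or* to *and*.
- Section 8.1 (statistical methods) carries this into the analysis: "The secondary hypothesis that the magnitude of responses for patients with PAD will be dependent on biological sex will be tested", using a time by group by sex analysis of variance. A time by type analysis of variance is added for PAD presentation. No outcome is listed for either.
- Section 8.2 (sample size): "Statistical significance will be set at a $P$ value of 0.05". No order of testing or division of alpha is given.
- Tukey's HSD is the only multiplicity device in 8.1. It is attached to the primary analyses of variance.
- Section 3.1.3 uses the exploratory label for acute exercise responses only.
- Section 3.1.1 ranks the variables for the primary objective: VO2peak first, 6MWT second, WIQ and SF-36 third. Section 4.1 nevertheless lists change in all four as primary endpoints.
- Section 2.2 gives the intended use: "determining if the magnitude of response is dependent on biological sex and presentation of PAD can help guide future research in determining optimal exercise prescriptions".

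**The concern.** A hypothesis that is to be tested at a fixed level needs a rule for what counts as support. Here two parts of that rule are missing: which outcome decides, and whether one factor or both must be positive. Tukey's HSD compares means within one analysis of variance, so it would not control error across outcomes or across the two factors even if it were extended to these analyses.

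Because both parts are open, they can be settled after the data are seen. At stake is a claim that response in PAD depends on sex or presentation, drawn from at most 28 PAD patients divided into two or three subgroups, and meant to steer later work on exercise prescription.

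This point is limited to the sex and type family. The ranking of the main endpoints, and the choice of model term or number of levels in the analyses of variance, are separate matters.

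**Working it through.** **Inputs from the documents.** Threshold 0.05 (8.2); two factors, sex and PAD type (3.1.2, 8.1); three PAD types (3.1.2); four outcomes in the primary analysis (8.1); 23 evaluable patients per group (8.2).

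**Assumptions, not in the documents.** Two-sided tests; 15 men and 8 women per group; PAD types of 8, 8 and 7; normally distributed change scores with an equal correlation ρ between outcomes; each outcome a single score; no true effect of sex or type.

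**Step 1. The plan's own figure.** With a 10 m difference and an SD of 12 m:

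n = 2 × (1.960 + 0.842)² × 12² / 10² = 2 × 7.85 × 1.44 = 22.6, so 23 per group.

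This reproduces the stated 23, and 23 × 1.2 = 27.6 gives the stated 28. The calculation concerns the PAD–CAD difference. The documents give no error rate or power for the secondary hypothesis.

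**Step 2. Independent tests.** P(at least one false positive in k tests) = 1 − 0.95^k.

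- Four outcomes × two factors, k = 8: 1 − 0.6634 = 33.7%.
- One factor over four outcomes, k = 4: 1 − 0.8145 = 18.5%.
- VO2peak only, either factor, k = 2: 1 − 0.9025 = 9.75%.
- Both factors positive, each on any of four outcomes: 0.1855² = 3.4%.
- Both factors positive on VO2peak only: 0.05² = 0.25%.

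**Step 3. Correlated outcomes.** Simulation of the planned interaction tests on change scores (time by group by sex; three-level time by type), 40,000 runs per row:

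| ρ | Any of 8 tests | Sex, any of 4 | Type, any of 4 | Both factors, any of 4 | VO2peak only, either factor |
|---|---|---|---|---|---|
| 0 | 33.7% | 18.4% | 18.6% | 3.3% | 10.0% |
| 0.3 | 32.1% | 17.6% | 17.4% | 3.0% | 9.9% |
| 0.5 | 28.9% | 15.5% | 15.8% | 2.4% | 9.8% |
| 0.7 | 25.2% | 13.3% | 13.5% | 1.6% | 9.7% |
| 0.9 | 18.5% | 9.4% | 9.9% | 0.8% | 9.8% |

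The documents give no correlation between outcome changes. The nearest figure is 0.557 in section 7.0, between the WIQ distance score and the 6MWT. It is cross-sectional and covers one pair, so 0.5 is only a plausible middle value.

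**Step 4. Sensitivity.**

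- A second simulation used 22 PAD patients only, a sex split of about 1:2, and one-way tests on change. It gave 33.6%, 32.2%, 29.8% and 25.4% at ρ = 0, 0.3, 0.5 and 0.7. The result hardly depends on which sex term is used.
- With SF-36 as two summary scores there are 5 × 2 = 10 tests: 40.1% if independent, 34.3% at ρ = 0.5. With eight SF-36 domains there are 11 × 2 = 22 tests: about 68% if independent, 53.2% at ρ = 0.5.
- The both-factors figures assume that neither factor matters. If one factor truly matters and is reliably detected, the chance of wrongly adding the other approaches the single-factor columns, about 9–19%.

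**Step 5. After the fix.** With two VO2peak tests and Holm, the smaller p-value must fall below 0.025. With no true effect, the chance of any false claim is 1 − 0.975² = 4.9% if independent, and at most 5% otherwise.

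**The case against.** The strongest reply is that the plan does not prescribe eight tests. Section 8.1 describes the primary analysis as a series over four named outcomes, but describes each secondary analysis in the singular and lists no outcome. Section 3.1.1 ranks VO2peak first, and 8.2 repeats the first two ranks. On that reading there are two tests and the figure is about 10%. The hypothesis in 3.2 also requires sex *and* type, which takes the figure below 5% when neither factor matters. Finally, strict family-wise control of secondary questions is not a universal requirement in a small, non-randomised cohort of 56, and the word secondary already subordinates them.

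Much of this stands. Testing across all four outcomes is an inference: a fair one, since 3.1.1 uses the same language of response magnitude for all four, but not a stated instruction. A reader might also infer that the protocol has no outcome hierarchy at all. It has one, under the primary objective; it is simply not carried to the secondary hypothesis, and 4.1 contradicts it.

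What does not stand is the conclusion that nothing is needed. The text does not choose among these readings. Even the VO2peak reading gives about twice 5% if either factor counts. And the remedy mainly asks for a deciding outcome and an honest label, not for full control over every secondary test.

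**Conclusion.** The point holds as an ambiguity with a range of consequences. The sex and type hypothesis is to be tested at 0.05 with no deciding outcome, no correction across outcomes or factors, and inconsistent wording on whether one or both factors are needed. The 30% figure is conditional on four single-score outcomes, any one positive counting, and moderate correlation; the subgroup sizes are assumed. More SF-36 or WIQ scores would raise it.

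Two stronger readings should be resisted. One is that the hypothesis will be falsely confirmed in about 30% of trials: that takes the *or* of 3.1.2 and all four outcomes as settled, and 3.2 says *and*. The other is that a false claim is likely: even at 30%, no false positive is the commoner result, and the stated use is mainly to guide further research.

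The matter affects a secondary claim, not the primary comparison. It is worth correcting because correction is cheap.

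**What to change.** In sections 3.1.2, 3.2 and 8.1:

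1. Name the interaction on month-6 change in VO2peak, already ranked first in 3.1.1, as the deciding test for sex and for PAD type.
2. State once, in the same words in all three places, whether either factor or both are needed. This is the investigators' choice. If either suffices, apply Holm over the two tests, which brings about 10% to about 5%. If both are required, each can be tested at 0.05.
3. Label the sex and type analyses of 6MWT, WIQ and QOL exploratory. Report estimates with 95% confidence intervals and make no claim of dependence from them.

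The cost is protocol wording, with no new data or patients. The downside is a slightly stricter threshold for the two VO2peak tests if Holm applies, and subgroup results on the other outcomes become hypothesis-generating.
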